**Figure:**

The following will be plotted by tumor type and treatment group.

- Percent change from baseline in target lesion tumor burden over time (ie, spider plot)
- Best percent change from baseline in target lesions (ie, waterfall plot)
- Kaplan-Meier plot of DOR for responders only
- Swimmer plot of DOR, and time on therapy for responders only
- Kaplan-Meier plot of PFS
- Kaplan-Meier plot of OS

**Listing:**

The following will be listed by tumor type and treatment group.

- Tumor lesion measurements
- Tumor evaluation at each visit, including non-target lesions and new lesions, tumor change from smallest sum of diameters in target lesions, and corresponding change (or percent change) from baseline
- Subject level efficacy for All Treated Subjects: BOR, OS, PFS, best response in target lesions, death indicator, duration of response for responders
- Survival - survival status, first dose date, last dose date, last known alive date, death date, time to death

**7.5.1      *Other Observations Related to Efficacy***

**Summary:**

- Certain efficacy analyses in [Section 7.5](#) are expected to be repeated by mutation status (eg, EGFR, BRAF), HPV status, IPI score, or other clinically meaningful disease characteristic, if there are sufficient data. These will be detailed in the DPP.

**Figure:**

- Certain efficacy plots may also be plotted by mutation status (eg, EGFR, BRAF), HPV status, IPI score, or other clinically meaningful disease characteristic, if there are sufficient data

**Listing:**

- FDG-PET
- Bone Marrow

## **7.6 Safety**

Analysis of safety will be based on All Treated Subjects and presented by tumor type, treatment arm and overall. Deaths and SAEs will be listed using All Enrolled Subjects.

Adverse events will be coded according to the most recent version of Medical Dictionary for Regulatory Activities (MedDRA) at the time of database lock and the severity will be graded using the NCI CTCAE version 4.0. Drug-related AEs are those events with relationship to study drug “Related” as recorded on the Case Report Form (CRF). If the relationship to study drug is missing, the AE will be considered as drug-related.

Listing of AEs will include all enrolled subjects as SAEs and deaths are collected pretreatment. Summaries of AEs will include (1) events occurring from the first dose date to 100 days (inclusive) after the last dose of either study drug for subjects who are off study treatment and (2) all events occurring from first dose date for subjects who are still on study medication, excluding the re-treatment period.

All recorded AEs will be listed and tabulated by system organ class (SOC), preferred term (PT), treated arm, and dose. When reporting AEs by CTC grade, summary tables will be provided based on the event with worst CTC grade (independent of relationship to study medication). Subjects will only be counted (1) once at the PT level, (2) once at the SOC level, and (3) once in the ‘Total subject’ row at their worst CTC grade, regardless of SOC or PT.

The analysis of laboratory results will be based on All Treated Subjects. Laboratory results will be categorized according to NCI CTCAE (version 4.0) grade. Summaries of laboratory results include baseline and (1) post-baseline results up to 100 days (inclusive) after the last dose of either study drug for subjects who are off study treatment and (2) all available post-baseline results for subjects who are still on study medication, excluding the re-treatment period.

### **7.6.1 Deaths**

#### **Summary:**

- All deaths during the study within 100 days after the last dose of either study drug will be summarized for cause of deaths by treatment group.

#### **Listing:**

- All recorded deaths for All Enrolled Subjects will be listed

### **7.6.2 Other Serious Adverse Events**

#### **Summary:**

The following will be summarized by tumor type, treatment arm and overall.

- Overall summary of SAEs by worst CTC grade (grade 1, 2, 3, 4, 5, unknown) presented by SOC/PT
- Overall summary of SAEs by worst CTC grade (any grade, grade 3-4, grade 5) presented by SOC/PT.
- Overall summary of drug-related SAEs by worst CTC grade (any grade, grade 3-4, grade 5) presented by SOC/PT.

**Listing:**

- By-subject SAE listing will be provided for the All Enrolled Subjects.

**7.6.3 Adverse Events Leading to Discontinuation of Study Therapies**

Adverse events leading to study drug discontinuation are AEs with action taken as “Drug was discontinued”.

**Summary:**

The following will be summarized by tumor type treatment arm and overall.

- Overall summary of AEs leading to discontinuation by worst CTC grade (grade 1, 2, 3, 4, 5, unknown) presented by SOC/PT.
- Overall summary of AEs leading to discontinuation by worst CTC grade (any grade, grade 3-4, grade 5) presented by SOC/PT.
- Overall summary of drug-related AEs leading to discontinuation by worst CTC grade (grade 1, 2, 3, 4, 5, unknown) presented by SOC/PT.
- Overall summary of drug-related AEs leading to discontinuation by worst CTC grade (any grade, grade 3-4, grade 5) presented by SOC/PT.

**Listing:**

- By-subject AEs leading to discontinuation listing will be provided.

**7.6.4 Overall Adverse Events**

**Summary:**

Adverse events and drug-related AEs will be tabulated by descending frequency of SOC and descending frequency of PT within each SOC, unless specified otherwise. The following will be summarized by tumor type, treatment arm and overall.

- Overall summary of any AEs by worst CTC grade (grade 1, 2, 3, 4, 5, unknown) presented by SOC/PT
- Overall summary of any AEs by worst CTC grade (any grade, grade 3-4, grade 5) presented by SOC/PT. This table will be restricted to events with an incidence greater or equal to 5% in any treatment arm.
- Overall summary of drug-related AEs by worst CTC grade (any grade, grade 3-4, grade 5) presented by SOC/PT.
- Overall summary of any non-serious AEs presented by SOC/PT. This table will be restricted to events with an incidence greater or equal to 5% in any treatment arm.

**Listing:**

- All recorded AEs occurring in the pretreatment, on-treatment, and post treatment period will be listed.

**7.6.5 Events of Special Interest**

The events of special interest (EOSI) consist of a list of preferred terms grouped by specific categories (endocrinopathies, infusion reactions, gastrointestinal, hepatobiliary, pulmonary,

renal, skin). These categories are defined by the Sponsor and the list that is most current at the time of analysis will be used. Changes may be made to this list with each new version of MedDRA and the final list used for the CSR will be included in an Appendix of the CSR.

**Summary:**

The following will be summarized by tumor type, treatment arm and overall.

- Overall summary of any EOSI by worst CTC grade presented by Category/PT (any grade, grade 3-4, grade 5).
- Overall summary of drug-related EOSI by worst CTC grade presented by Category/ PT (any grade, grade 3-4, grade 5).
- Overall summary of any serious EOSI by worst CTC grade presented by Category/PT (any grade, grade 3-4, grade 5).
- Overall summary of any EOSI leading to discontinuation by worst CTC grade presented by Category/PT (any grade, grade 3-4, grade 5).
- Overall summary of drug-related EOSI leading to discontinuation by worst CTC grade presented by Category/PT (any grade, grade 3-4, grade 5).

**Listing:**

- EOSI definition
- Listings for the EOSI will be provided by subject and dose.

**7.6.6     Multiple Events**

Analyses that take into account the multiple occurrences of a given AE will be conducted. In order to prepare these analyses, the CRF data will be processed according to standard BMS algorithms in order to collapse AE records into unique records based on the PT. This data will be presented as the rate per 100 person-years. These analyses will take into account all on-treatment events (allowing more than 1 event per subject) and the total duration of AE follow-up that is based on exposure to the study medication. The person-year exposure will be computed as the sum over the subjects' follow-up expressed in years and is defined as:

- Date of last dose of study treatment - date of first dose of study treatment + 100 +1 days, for subject who are off study treatment and were followed for at least 100 days after last dose of study medication.
- Last known date alive - date of first dose of study medication +1, for subjects who are still on-treatment or who are off study treatment and were followed less than 100 days after last dose of study medication.

When specified, the 95% CI of the rate per 100 person-years of exposure will be derived using normal approximation and variance estimation proposed in Cook and Lawless.

**Summary:**

The following summary tables will be provided:

- Total number and rate (exposure adjusted) of occurrences for all AEs.

- For EOSI:
  - Frequency of unique AEs, meaning the number of subjects experiencing an AE once or multiple times by tumor type, treatment arm, and overall

**Listing:**

- Unique instances of all AEs, ie, after duplicates have been eliminated and overlapping and contiguous occurrences of the same event (ie, same PT) have been collapsed.

**7.6.7 Clinical Laboratory Evaluations**

Clinical laboratory data will be first analyzed using International System of Units (SI). Analyses may be repeated using US conventional units. In addition, further analyses on specific laboratory parameters will be performed by treatment group and is described in Sections 7.6.7.1 and [7.6.7.2](#).

**Summary:**

The number (%) of subjects with the following will be summarized by tumor type, treatment group and overall, if appropriate, using the worst CTC grade on-treatment per subject.

- Post-baseline grade
- Shift-table of worst on-study CTC grade compared to baseline CTC grade

**Listing:**

- A by-subject listing of these laboratory parameters will be provided.
- Laboratory abnormality criteria
- Laboratory results outside of normal range

**7.6.7.1 Abnormal Hepatic Function Test**

**Summary:**

The number of subjects with the following laboratory abnormalities from on-treatment evaluations will be summarized by tumor type, treatment group, and overall.

- ALT or AST > 3 x ULN, > 5 x ULN, > 10 x ULN and > 20 x ULN
- Total bilirubin > 2 x ULN
- Concurrent (within 1 day) ALT or AST > 3 x ULN and total bilirubin > 2 x ULN
- Concurrent (within 30 days) ALT or AST > 3 x ULN and total bilirubin > 2 x ULN

**Figure:**

The following scatter plots will be produced for the following hepatic laboratory parameters. On-treatment peak total bilirubin and on-treatment peak AST/ALT may or may not happen on the same day of liver testing.

- Total bilirubin peak vs. AST peak
- Total bilirubin peak vs. ALT peak

**Listing:**

- A by-subject listing of these specific abnormalities will be provided.

### **7.6.7.2 *Abnormal Thyroid Function Test***

#### **Summary:**

The number of subjects with the following laboratory abnormalities from on-treatment evaluations will be summarized by tumor type, treatment group, and overall.

- TSH value > ULN and
  - with baseline TSH value  $\leq$  ULN
  - at least one T3/T4 test value  $<$  LLN
- TSH  $<$  LLN and
  - with baseline TSH value  $\geq$  LLN
  - at least one T3/T4 test value  $>$  ULN

#### **Listing:**

- A by-subject listing of these specific abnormalities will be provided.

### **7.6.7.3 *Other Observations Related to Laboratory Values***

- Time to onset Liver Function Test (LFT) elevation
- Time to onset LFT from latest dose
- Time to onset Thrombocytopenia
- Time to onset Neutropenia
- Time to resolution of LFT from first dose
- Time to resolution of Neutropenia
- Time to resolution of Thrombocytopenia
- Steroid use % of subjects
- LFT elevation Hepatotox medication use
- Patients with Neutropenia grade  $\geq 2$  and GCSF treatment
- Neutropenia grade  $\geq 2$  and temp elevation
- Patients with simultaneous occurrence of toxicity elevations

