^a If 4 subjects are enrolled in a cohort, the decision to enroll additional patients or escalate will be made after the 3rd evaluable subject completes the DLT window. In this situation, if the decision is made to remain at the same dose level and the 4th subject is evaluable, he/she will be included as part of the 2nd cohort at that dose level

If either Cohort 1 or Cohort 2 exceeds the MTD, alternate treatment regimens may be explored during dose escalation or cohort expansion (listed in Table 3.1.5-3).

Table 3.1.5-3: Alternate Treatment Regimens

Cohort Designation	urelumab	nivolumab ^a
A ^b	8 mg IV every 8 weeks	3 mg/kg or 240 mg IV every 2 weeks
B ^b	8 mg IV every 8 weeks	1 mg/kg or 80 mg IV every 2 weeks
C	3 mg IV every 4 weeks	1 mg/kg or 80 mg IV every 2 weeks

Table 3.1.5-3: Alternate Treatment Regimens

Cohort Designation	urelumab	nivolumab ^a
D ^b	3 mg IV every 8 weeks	3 mg/kg or 240 mg IV every 2 weeks

^a Nivolumab 1 mg/kg or 3 mg/kg will be administered for subjects enrolled prior to Revised Protocol 02. Nivolumab 80 mg or 240 mg flat dose administered for subjects enrolled after Revised Protocol 02

^b Dosing regimen not applicable following Revised Protocol 03 (Dated 31-Aug-2015)

All available clinical and laboratory data observed during dose escalation will be reviewed to determine the alternative treatment regimen listed in [Table 3.1.5-3](#) to be evaluated. The nature, time of onset, and time to resolution of DLTs observed will be reviewed in the context of the current safety data from the respective urelumab and nivolumab trials. After review of this data, and after consultation between the investigators and the sponsor, the identified alternative treatment regimens may be evaluated.

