### **6.1.2 *Treatment Period***

- Begins when the subject is assigned to a treatment arm
- Consists of up to 6 eight-week treatment cycles (48 weeks)
  - Nivolumab will be given every 2 weeks
  - Urelumab will be given every 4 weeks
  - On days where both study drugs are given, nivolumab will be given first followed by urelumab within 30 minutes of completing the infusion of nivolumab
  - Subjects may continue additional cycles of study therapy, up to a maximum of 6 cycles, on a case-by-case basis
- This period ends when the subject is discontinued from study therapy

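### Time to resolution of liver-test elevations runs from first dose, so the summary is latency plus duration and does not show how long elevations last

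*SAP*

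**What the plan says.** SAP 7.6.7.3 is a short bullet list of laboratory observations. Its liver items on timing are "Time to onset Liver Function Test (LFT) elevation", with no origin given; "Time to onset LFT from latest dose"; and "Time to resolution of LFT from first dose". The second item shows that the phrase naming a dose sets the time origin, so the first-dose origin for resolution is a stated choice. The parallel items, "Time to resolution of Neutropenia" and "Time to resolution of Thrombocytopenia", state no origin.

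The section does not say which grade counts as an elevation, what counts as resolved, which episode is used, or what happens to elevations that have not resolved.

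The other liver outputs, in SAP 7.6.7 and 7.6.7.1, are worst-grade and shift tables, counts above multiples of the upper limit of normal, scatter plots of peak values and by-subject listings. None of the summaries measures onset to resolution.

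Elsewhere the documents treat onset and resolution as two quantities. On choosing an alternative regimen, Protocol 3.1.5 says: "The nature, time of onset, and time to resolution of DLTs observed will be reviewed in the context of the current safety data". The SAP repeats this under its Table 4.

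**The concern.** A reader who sees time to resolution takes it to mean how long the abnormality lasted. Measured from first dose, it mainly reflects when the abnormality began, because onset can occur at any point in a long treatment period while the elevation itself may be short. Two groups with the same duration but different latency would show different resolution times, and the group with earlier onset would look as if it recovered faster.

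The item matters more for the liver than for most laboratory tests. Protocol 1.4.3 and 1.5 name hepatotoxicity as the most frequent clinically significant drug-related event with urelumab. Protocol 1.5 and 4.5.5 to 4.5.7 tie dosing delays and discontinuation to recovery and to how long a delay lasts. A summary of how long elevations last is what a reader of the safety report would look for, and the listed summaries do not supply it.

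**Working it through.** The documents give no figure for this quantity, so there is nothing to reproduce. The check is an identity followed by illustrations. All latencies and durations below are assumed.

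**Identity.** For one subject and one elevation:

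(resolution − first dose) = (onset − first dose) + (resolution − onset) = latency + duration.

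**Range of latency.** SAP 6.1.2 allows up to six 8-week cycles, 48 weeks or 336 days. For subjects off treatment, SAP 7.6 then includes "post-baseline results up to 100 days (inclusive) after the last dose of either study drug". Latency can therefore be much larger than duration.

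**Same duration, different onset.** Assumed duration 28 days:

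| Onset (day) | Reported from first dose | Ratio to true duration |
|---|---|---|
| 14 | 14 + 28 = 42 | 1.5 |
| 56 | 56 + 28 = 84 | 3 |
| 112 | 112 + 28 = 140 | 5 |
| 224 | 224 + 28 = 252 | 9 |

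Measured from onset, all four give 28.

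**The order can reverse.** Onset on day 14 lasting 28 days gives 42. Onset on day 56 lasting 14 days gives 70. The longer elevation has the smaller value. Both onsets fall within 8 weeks of first dose (8 × 7 = 56 days).

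**Groups of events.** I drew 200,000 events per group. Duration was exponential with median 28 days, rounded up to the next weekly test, which gives a median of 35 days on the weekly grid.

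- Onset uniform over days 7–56: median from first dose about 65 days.
- Onset uniform over days 57–336: median from first dose about 240 days, with the same duration distribution.
- Early group with durations doubled (median 70 days): median from first dose about 96 days, still well below 240.
- Onset uniform over days 7–336: latency makes up about 85% of the variance of the first-dose measure (0.847). Its correlation with true duration is √(1 − 0.847) = 0.39.

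**Can duration be recovered from the summaries?** Not from medians. Take three subjects with onsets on days 14, 56 and 224 and durations of 56, 14 and 28 days. Their first-dose times are 70, 70 and 252. Median resolution minus median onset is 70 − 56 = 14, whereas the median duration is 28. Means do subtract, but only if the same subjects enter both summaries, the onset item also runs from first dose, and every elevation has resolved. The SAP settles none of these.

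**The case against.** The strongest reply is that little depends on this line. It is one bullet under other observations, with no statistic or test attached. Protocol 1.2 as given in the synopsis states that no formal primary hypothesis is tested, and primary safety rests on incidence. That stands, and it limits the weight of the point.

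A reader might infer that the first-dose origin could mislead the choice of dose or schedule. The documents do not support that. The regimen review in Protocol 3.1.5 draws on all available clinical and laboratory data, and nothing says it uses this output. No between-regimen inference is planned. In the Protocol's tables the regimens still applicable after Revised Protocol 03 all give urelumab every 4 weeks, and escalation cohorts hold at most about 12 subjects. Severe events are also few: Protocol 1.5 reports grade 3/4 ALT and AST elevations of 2% each in 138 patients, about 0.02 × 138 ≈ 3 subjects each. Any-grade counts are not given.

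A reader might also infer that duration is lost. It is not. Weekly tests and the by-subject listings in SAP 7.6.7 and 7.6.7.1 allow it to be derived subject by subject. SAP section 9 defers the complete list of analyses to a Data Presentation Plan that was not supplied, so an onset-based output may exist there.

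Finally, the bullet states its origin, so a careful reader is warned, and time from first dose to recovery has some descriptive use. Both are fair. Neither makes it a measure of how long elevations last.

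**Conclusion.** The point holds in a limited form. As written, the summary is latency plus duration, and this follows from the definition alone. That early-onset elevations look quicker to resolve is conditional: it holds when durations are similar, and it can hold when early events last longer. The sizes shown rest on assumed latencies and durations and are not predictions for this trial.

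One descriptive safety summary is affected. DLT rules, sample size and the primary incidence summaries are not. The neutropenia and thrombocytopenia items should not be read as sharing the fault. They state no origin, which is a gap to fill rather than a wrong choice. The change is still worth making, because it concerns urelumab's main identified toxicity and needs no new data.

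**What to change.** In SAP 7.6.7.3, define time to resolution of a liver-test elevation as the resolution date minus the onset date of that elevation, and state:

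- the onset grade, for example Grade 2 or higher, and which analytes count;
- resolution as return to Grade 1 or less or to baseline, for analysis only. Protocol 4.5.6 uses similar terms as a condition for resuming treatment, and that clinical rule is not touched;
- the rule for repeat episodes, for example first or worst episode per subject;
- censoring of unresolved elevations at the last test, with Kaplan-Meier if numbers allow and a listing otherwise.

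If the first-dose version is kept, label it as time from first dose to recovery. State the onset origin for the neutropenia and thrombocytopenia items as well.

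The dates are already collected. Protocol 5.3.1 has liver tests weekly during urelumab and for 8 weeks after its last dose, so onset and resolution are known to about a week in that period and less closely afterwards. The cost is a few added definitions and slightly more programming.

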### **7.6.8 *Electrocardiograms***

#### **Listing:**

- A by-subject listing of all ECG measures
- A listing of only abnormal ECG interpretations

### **7.6.9 *Vital Signs and Physical Findings***

#### **Summary:**

The following parameters and their corresponding change from baseline will be summarized by timepoint and treatment group.

- Vital Signs

- Body weight and performance status

**Listing:**

- Vital Signs
- Height, body weight and performance status
- Abnormal physical examination findings

**7.6.10 Other Observations Related to Safety**

**Listing:**

The following by-subject listings will be produced if data exists.

- Pulse Oximetry
- Abnormal Chest X-Ray
- Abnormal Bone Scan
- Abnormal Brain Scan
- Diagnostic and medical procedures
- Pregnancy

**7.7 Pharmacokinetic Analyses**

The PK parameters and concentration data of urelumab and nivolumab will be summarized and listed by tumor type, treatment arm and sampling time. PK concentrations may be used in combination with other studies for exposure-response or population PK modeling, which will be part of a separate report.

**7.7.1 Pharmacokinetic Concentrations**

**Summary:**

Summary statistics will be provided for the following pharmacokinetic serum concentrations by tumor type, dose, regimen, study day and time based on the Urelumab PK Subjects and Nivolumab PK Subjects.

- Serum concentrations of Urelumab
- Serum concentrations of Nivolumab

**Figure:**

Plots of the following concentration vs. cycle by dose and regimen

- Serum concentrations of Urelumab
- Serum concentrations of Nivolumab

**Listing:**

- Urelumab and nivolumab serum concentrations

